6.2 Intent-to-treat incidence rate ratios comparing product use groups to the control group

IRRs with 95% confidence intervals will be calculated comparing each product use group (groups 2-4) to the control group (group 1) using the IR function in STATA. In addition, IRRs with 95% confidence intervals will be calculated comparing each vaginal probiotic group (group 3 and 4) to the metronidazole group (group 2). As before, these IRRs will be calculated for each primary efficacy outcome and for each of the three time periods: between the Enrolment visit and the M2 visit (during product use), between the M2 visit and M6 visit (after cessation of product use) and for the entire study period after randomisation. They will be reported in the following table (one table for each time period):

	Group 2 vs 1 IRR (95% CI)	Group 3 vs 1 IRR (95% CI)	Group 4 vs 1 IRR (95% CI)	Group 3 vs 2 IRR (95% CI)	Group 4 vs 2 IRR (95% CI)
Incident BV by					
modified Amsel					
criteria					
Incident Nugent 4-10					
Incident Nugent 7-10					
Incident TV by culture					
Incident symptomatic					
vaginal candidiasis					

6.3 Per protocol incidence rate ratios comparing product use groups to the control group

A few significant protocol deviations occurred that could have an impact on the primary analysis results:

- CT/NG PCR testing was not available at the RU clinic and was outsourced to the National Reference Laboratory in Kigali, Rwanda. Test results were usually available only weeks after sample collection. We realised that this might be an issue early on and increased the sample size of each randomisation group to 17 instead of 15 to allow for exclusion of women who were randomised while having an ongoing CT or NG infection. Unfortunately, the number of women with a CT or NG infection in each randomisation group turned out to be higher than expected: 8/17 in Group 1, 7/17 in Group 2, 4/17 in Group 3, and 7/17 in Group 4 (Fisher's exact p = 0.53).
- Discrepancy between modified Amsel criteria and Nugent score at the Enrolment visit: Women could be enrolled if they had negative modified Amsel criteria after having completed the 7-day metronidazole treatment. Nugent scores became available later. In a handful of cases, women who were randomised because they no longer had BV by modified Amsel criteria turned out the have a Nugent score of 7-10 at the Enrolment visit.
- 3. Another special case is the use of antibiotics and/or antifungals during follow-up. If these were prescribed by the study physician due to symptomatic BV, TV, or symptomatic vaginal candidiasis, their use is causally related to the primary endpoints. These women will therefore be included in the per protocol analyses. However, if women used antibiotics and/or antifungals extensively during follow-up, including for reasons not related to the primary endpoints, they may be excluded in the per protocol analyses. This will be determined on a case-by-case basis by the Chief Investigator and each case will be described.

The analyses described in 6.1 and 6.2 will be repeated after exclusion of the participants described in 1, 2, and 3 above. If additional significant protocol deviations are discovered during data analyses (which is unlikely), additional exclusions might be made. These will also be determined on a case-by-case basis and each case will be described.

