4.3 Sample size

This pilot study is descriptive and one of its aims is to inform sample size calculations of a future efficacy trial. Formal sample size calculations were therefore not performed. In the clinical trial, 60 women will be randomised into 4 groups consisting of 15 women each. Based on previous experiences with reproductive health clinical trials in the same study population, we expect to have to screen at least 120 women to enrol 60.

In the qualitative research, the number of FGDs or IDIs held will be governed by data saturation: no new discussions/interviews will be done when they no longer generate new information. The sample sizes listed in this study protocol are estimates based on our previous experiences with qualitative research. For feasibility objective 1, we expect to conduct quantitative face-to-face interviews with at least 30 women attending recruitment sessions who did not pass pre-screening (in addition to the approximately 120 women attending screening visits) and conduct 2 FGDs with women enrolled in

the trial. For feasibility objective 2, we expect to conduct 2 FGDs and 5 IDIs (in addition to quantitative face-to-face interviews with the 60 women enrolled in the trial). For feasibility objective 3, we expect to conduct one FGD with all 12 women in the frequent sampling subgroup. For feasibility objective 5, we expect to conduct 5 IDIs with clinicians and policymakers. The total number of FGDs and IDIs will therefore be approximately 5 FGDs and 10 IDIs.

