5.2 Eligibility criteria

Inclusion criteria:

- Female, 18-45 years old
- Sexually active, defined as having had sex at least twice in the two weeks prior to screening
- At high risk of HIV/STIs/BV, defined as having had more than one sexual partner in the last 12 months OR having been treated for an STI and/or BV in the last 12 months
- Successfully treated for BV by Amsel criteria or TV (defined as no BV by Amsel criteria and no TV on wet mount at the enrolment visit) and free of HIV (at screening), pregnancy (at screening and the enrolment visit), symptomatic vaginal candidiasis and UTI (at the enrolment visit), and syphilis, NG, and CT (at the results visit). Due to the long turn-around time for NG and CT lab test results, women may be enrolled when their NG and CT results are not yet known, but a new participant will be randomised for each woman whose screening sample comes back positive for NG and/or CT after having been randomised. The NG/CT-positive women will be allowed to complete the study but their data may be removed from some analyses.
- Currently in good physical and mental health as judged by a study physician
- Willing and able to adhere to study procedures and provide written informed consent.

According to Rwandan ethics guidelines, unmarried women aged 18-20 also need the written informed consent of a parent or guardian.

 Women are allowed to use contraception, including hormonal contraception; use of these methods will be taken into account in the instructions given to women about probiotic use and in the data analysis.

Exclusion criteria:

- HIV positive
- Pregnant
- Clinician-observed genital ulcers, condylomata, or other genital abnormalities at screening and/or enrolment
- Underwent a gynaecological surgery/invasive procedure in the 3 months prior to screening
- History of significant urogenital prolapse, undiagnosed vaginal bleeding, urine or faecal incontinence, or blood clotting disorders
- Allergic to metronidazole or any other components of the study drugs
- Not willing to stop use of other oral or vaginal probiotics from the screening visit until the end
 of study participation
- Participating in another health intervention study
- For any other reason potentially interfering with participant safety or protocol adherence as judged by the Principal Investigator (these reasons will be recorded)

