6.3 Results visit

All HIV-negative, non-pregnant women regardless of eligibility up to that point will be asked to return to the study clinic 1-2 weeks after the screening visit to obtain their screening test results.

The following procedures will take place at the results visit:

- 1. Confirmation of contact information;
- 2. Provision of HSV-2, syphilis, NG, CT, and TV culture results.
 - If syphilis, NG or CT positive or received treatment for candidiasis at screening (regardless of other test results): Treat STIs according to national guidelines and ask the woman to return to RU as soon as possible after completing her STI treatment for a repeat wet mount. Women who received candidiasis treatment at screening can provide a repeat wet mount at this visit. Vaginal swabs to measure vaginal pH and prepare a wet mount (as well as a slide for Gram stain Nugent scoring) will be obtained without speculum. If negative for BV by Amsel criteria and TV on wet mount, the woman is not eligible for enrolment. If positive for BV by Amsel criteria and/or TV on wet mount, treat using oral metronidazole for 7 days and schedule the enrolment visit within 3 days of completing treatment.
 - If TV culture positive and not yet treated for TV (based on wet mount) at screening: treat using oral metronidazole for 7 days and schedule the enrolment visit within 3 days of completing this treatment.
 - If BV by Amsel criteria at screening and not yet treated (regardless of symptoms): treat using oral metronidazole for 7 days and schedule the enrolment visit within 3 days of completing this treatment.
 - A positive HSV-2 result will not have any treatment or eligibility consequences.
- 3. Due to the logistics of NG/CT PCR, we expect long turn-around time. For this reason, and because the prevalence of NG and CT is much lower than the prevalence of the other STIs, women may be enrolled when their NG and CT results are not yet known. However, a new participant will be randomised for each woman whose screening sample comes back positive for NG and/or CT after having been randomised. The NG/CT-positive women will be allowed to complete the study but their data may be removed from some analyses.
- 4. Due to the logistics of Nugent scoring, Nugent scores may not be available at the enrolment visit. Results will not be used to guide enrolment and treatment decisions anyway, but will only be used in the data analysis.

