1.1 Study overview

A flow diagram of study visits, and numbers of women seen at each visit, is shown in Figure 1. Women at high risk for HIV, sexually transmitted infections (STIs), and BV were targeted using community mobilisers who were high risk women themselves. Women who were potentially eligible (HIV-negative, non-pregnant, aged 18-45, and sexually active with high risk of HIV/STI/BV) and interested in participating were invited to visit the RU clinic for screening procedures. Please refer to the study protocol for a full listing of eligibility criteria. At the screening visit, a face-to-face interview, speculum examination, and testing for HIV, pregnancy, urinary tract infection (UTI), BV (by Amsel criteria and Nugent scoring), and *Trichomonas vaginalis* (TV; by wet mount and InPouch culture) were conducted. At the end of the visit, preliminary eligibility was assessed, and initial treatments and referrals were given based on available test results. Additional STI testing was conducted on stored samples after the participant had left the clinic. Results of those tests were given as required, and eligibility was reassessed. At the end of the Screening and Results Visits cascade, women were either declared ineligible or diagnosed with BV by Nugent score and/or TV on wet mount or by culture and treated with 500mg oral metronidazole twice per day for 7 days.

At the Enrolment Visit, only women whose BV/TV treatment had been successful (no BV by Amsel criteria and no TV on wet mount), who were still not pregnant, and who were free of STIs and UTI, were randomised to 4 groups as follows:

Group 1) Behavioural 'vaginal practices cessation and safer sex' counselling only (also referred to as the 'control group');

Group 2) Behavioural counselling plus oral metronidazole 500mg, twice per week for two months; Group 3) Behavioural counselling plus Ecologic Femi vaginal capsule, once per day for 5 days immediately after oral metronidazole treatment followed by thrice weekly for two month;

Group 4) Behavioural counselling plus Gynophilus vaginal tablet, once every 4 days for two months. Participants took/inserted the first dose of their intervention (if applicable) under direct observation at the Enrolment Visit.

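### The 'per protocol' analysis in SAP 6.3 pools two baseline restrictions, mislabelled as protocol deviations, with an undefined post-randomisation exclusion, and it has no product-use rule

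*SAP*

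**What the plan says.** SAP 6.3 opens: "A few significant protocol deviations occurred that could have an impact on the primary analysis results". Three numbered items follow.

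1. **CT/NG infection.** PCR results arrived weeks after sampling. The team "increased the sample size of each randomisation group to 17 instead of 15" so that infected women could be left out. The counts were "8/17 in Group 1, 7/17 in Group 2, 4/17 in Group 3, and 7/17 in Group 4 (Fisher's exact p = 0.53").
2. **Nugent 7-10 at Enrolment** in women with negative modified Amsel criteria. The number is given only as a handful.
3. **Antibiotic or antifungal use during follow-up**, called a special case. Women treated by the study physician for an endpoint infection stay in. Women with extensive use, including for unrelated reasons, may be taken out. The Chief Investigator decides case by case, and each case is to be described.

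Then: "The analyses described in 6.1 and 6.2 will be repeated after exclusion of the participants described in 1, 2, and 3 above". If more deviations emerge during data analysis, which the SAP calls unlikely, more exclusions may follow, again case by case.

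On item 1, Protocol 5.2 lists freedom from NG and CT among the inclusion criteria but adds an exception: "women may be enrolled when their NG and CT results are not yet known". A woman who later proves positive may complete the study, a further woman is to be randomised for her, and her data may be left out of some analyses, which are not named.

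On item 2, Protocol 5.2 defines successful treatment by Amsel criteria and wet mount. Of Nugent scores, Protocol 6.3 says: "Results will not be used to guide enrolment and treatment decisions anyway". It reserves them for the data analysis.

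SAP 6.4 derives a product adherence figure from 0 to 100% for each woman. It is plotted and used as a GEE covariate. SAP 6.3 does not use it.

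**The concern.** A 'per protocol' incidence rate ratio comparing product groups with control will be read as the effect when products are used as directed. A set with no product-use rule cannot support that reading.

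The other useful reading is the effect in women free of CT/NG, and of Nugent-defined BV, at the start. The first two exclusions alone would give that estimate, because a subset defined before randomisation keeps the comparison between groups. Adding an exclusion based on what happened after randomisation can undo this. Antibiotic and antifungal use in follow-up may depend on the assigned product and on the outcome, since symptomatic BV and candidiasis are treated with these drugs.

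According to Protocol 3.2 the pilot data will be used to choose interventions for a later efficacy trial. A misread ratio could influence that choice.

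**Working it through.** **1. The one computed figure in SAP 6.3.** The SAP gives Fisher's exact p = 0.53 for CT/NG across groups. With table probability ∏C(17, xᵢ)/C(68, 26), summed over all tables no more probable than 8, 7, 4, 7, full enumeration gives p = 0.544. The mid-p version gives 0.514 and Pearson chi-square 0.524. The printed value is not reproduced, but the difference is immaterial and nothing below rests on it.

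**2. What each exclusion is.**

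| Exclusion | When determined | Protocol position | Rule |
|---|---|---|---|
| 1. CT/NG positive | Screening sample, before randomisation | Randomisation allowed while results pending; removal from some analyses foreseen | Objective (PCR) |
| 2. Nugent 7-10 | Enrolment swab, before randomisation (Protocol 6.4, steps 4 and 5) | Not an enrolment test; analytic use foreseen | Objective (score) |
| 3. Extensive antibiotic/antifungal use | After randomisation | Treatment of infections in follow-up allowed (Protocol 4.1) | Undefined; Chief Investigator decides |
| Catch-all | During data analysis | Not applicable | Undefined; case by case |

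No row concerns product use. The wording of exclusion 3 also leaves its boundary open. Use prompted by an endpoint infection keeps a woman in, yet extensive use that includes other reasons may remove her, so outcome-related courses may count towards 'extensive'. Under Protocol 9 the Chief Investigator or a designee also carries out the analysis. Protocol 4.4 states blinding only for laboratory technicians.

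**3. Set sizes.** Exclusion 1 removes 8 + 7 + 4 + 7 = 26 of 68 women (38%). This leaves 17 − 8 = 9, 17 − 7 = 10, 17 − 4 = 13 and 17 − 7 = 10, in total 42. Exclusion 2 has no count. If it were 3 to 6 women, none of them CT/NG positive (an assumption), 39 to 36 would remain.

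**4. Precision of the restricted set.** With equal rates and equal follow-up per woman, cases are proportional to women, so the standard error of log IRR against control grows by √[(1/9 + 1/n)/(1/17 + 1/17)].
- Groups 2 and 4 (n = 10): √(0.2111/0.1176) = 1.34.
- Group 3 (n = 13): √(0.1880/0.1176) = 1.26.

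This is the price of exclusion 1. It does not measure the fault described here.

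**5. What one discretionary exclusion could do.** The documents give no case counts. Assume one incident case at most per woman, 5 cases in 9 controls, 3 in 10 women in Group 2, and equal follow-up.
- Start: (3/10)/(5/9) = 0.54.
- One Group 2 case removed: (2/9)/(5/9) = 0.40.
- One control case removed: (3/10)/(4/8) = 0.60.

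With 4 cases in each group the ratio starts at (4/10)/(4/9) = 0.90 and becomes (3/9)/(4/9) = 0.75 or (4/10)/(3/8) = 1.07. These figures only illustrate sensitivity in sets this small. They do not estimate a bias.

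**The case against.** The defence is substantial.

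- **The protocol foresaw these exclusions.** A reader might infer that dropping CT/NG-positive women contradicts the protocol. It does not: Protocol 5.2 says their data may be removed from some analyses, and Protocol 6.3 reserves Nugent for analysis. Excluding a woman who starts at Nugent 7-10 is also sensible, since under SAP 6.1 she cannot count as an incident Nugent 7-10 case at the next visit unless adequately treated.
- **There was a departure over CT/NG, but not by these women.** The protocol asks for one replacement per positive woman. The SAP added 68 − 60 = 8 women against 26 positives. The replacement rule was not met, so speaking of a deviation has some basis. It still does not turn women enrolled under an explicit exception into deviators.
- **Exclusion 3 may be empty.** SAP 6.4 expects too few extensive users to assess for effect modification or confounding. If there are none, and no catch-all exclusions, the set is already the baseline-restricted one.
- **Other results exist.** SAP 6.1 and 6.2 are untouched, and SAP 6.4 handles CT/NG by exclusion from, or adjustment in, the GEE models. It would be wrong to infer that the trial is left without a clean result.
- **Non-adherent women are not shown to be retained.** No adherence counts are given, and the catch-all could in principle remove such women, though it states no rule.
- **Entry on Nugent alone.** SAP 1.1 describes women as "diagnosed with BV by Nugent score and/or TV on wet mount or by culture", whereas Protocol 5.2 refers to BV by Amsel criteria or TV. It is tempting to add these women to the departures that 6.3 overlooks. The documents give no count and do not show whether an amendment covers the change, so the point is not pressed.

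All of this narrows the concern. It does not answer the misleading label or the pooling of exclusions of two different kinds.

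**Conclusion.** The concern holds as a fault of labelling and construction in a supportive analysis. SAP 6.3 describes as protocol deviations two baseline conditions under which the protocol permitted randomisation. It gives the name 'per protocol' to a set with no product-use rule. It also merges exclusions that preserve the randomised comparison with exclusions that may not.

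The possible selection bias cannot be sized. It depends on how many women leave under exclusion 3 or the catch-all, and on whether their removal is related to group and outcome. It is nil if nobody leaves that way. The 38% loss and the factors of 1.34 and 1.26 might be read as the size of the problem, but they come from exclusion 1 and remain after the fix.

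The judgement that exclusions 1 and 2 keep a randomised comparison assumes that they are applied strictly from the Screening and Enrolment samples, in the same way in every group.

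**What to change.** - Rename SAP 6.3 'baseline-restricted sensitivity analysis'. Apply exclusions 1 and 2 only, state the number of women per group, and stop describing these two conditions as protocol deviations.
- Report exclusion 3, and any catch-all exclusions, as a separate additional run labelled as not protected by randomisation. Define 'extensively' in the SAP, say whether courses given for endpoint infections count, and have the cases chosen by someone blind to group and outcome. SAP 3.1 already tabulates Month 6 attendance, so the definition would be written after follow-up. That makes the blinding matter more.
- Do not add a per-protocol set based on an adherence threshold. SAP 6.4 sets Group 1 adherence at 100%, so a cut would remove women only from Groups 2 to 4, which is itself a one-sided post-randomisation exclusion.

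The cost is SAP wording and one more run of existing code on small sets. No new data are needed and no planned exclusion is lost.

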6.4 Adjustment for confounding: generalised estimating equation (GEE) models

Other behavioural and clinical characteristics might also influence the primary efficacy outcomes. Some of these variables were collected at baseline but also at the M2 and M6 visits.

Sexual behaviour	Baseline	M2	M6	p-value ²
Number of sex partners in last month at baseline or per				
month during follow-up period (median, IQR)				
Currently has a main sex partner (n %) ¹				
Obtained a new main partner during period (n %)	NA			
Lives together with main sex partner (n %)				
Main sex partner circumcised (n % per category)				
- Yes				
- Does not know				
- No				

We will assess any behavioural changes over time in the total study population as follows:

Main sex partner has other sex partners (n % per category)				
- Yes				
- Does not know				
- No				
Vaginal sex frequency last 2 weeks (median, IQR)				
Any condom use in past two weeks (n %)				
Exchanged sex for money/goods in past month (n %)				
Contraceptive practices, vaginal practices, menses	Baseline	M2	M6	p-value ²
Currently using a modern method of contraception other				
than condoms (n % per category):				
- Pills				
- Injections				
- Implant				
- Copper IUD				
- Sterilised				
- Other				
Weekly frequency of vaginal practices since the last visit				
(includes water only using fingers, water and soap using				
fingers, paper/cloth/cotton wool with or without liquid, and				
traditional herbs, stones, or powders)				
Amenorrhea due to hormonal contraception (n %)				
Amenorrhea due to other reason (n %)				
If no amenorrhea, duration of bleeding (median, IQR)				
If no amenorrhea, any vaginal sex during menses (n %)				

1. If missing values, a footnote detailing the number of missing values for a particular variable will be added to the table.

2. McNemar's test for binary or categorical variables and Wilcoxon test for medians.

We will use generalised estimating equation (GEE) models with Nugent 4-10 (compared to Nugent 0-3) at any study visit after randomisation as the outcome and randomisation group as the main predictor (and indicator variable with Group 1 as the reference group) to adjust for the potential effects of these characteristics. A similar model will be run with Nugent 7-10 (compared to Nugent 0-6) as the outcome.

Assessment for effect modification:

We will assess CT and NG infection at Screening (combined variable: one or both infections diagnosed by PCR at Screening and not treated until later on in the study) for effect modification. If statistically significant effect modification is present, the relevant women will be excluded from the GEE models. If no effect modification is present, the presence of CT and/or NG infection will be adjusted for (see below). We expect the number of women with a Nugent score of 7-10 at the Enrolment visit, or who used antibiotics and/or antifungals extensively, to be too small to assess for effect modification or confounding.

Adjustment for confounding:

Since the sample size of the Rwanda VMB Study is small, we do not have sufficient statistical power to adjust for many confounding variables. We will focus on two variables: CT/NG infection (see above) and study product adherence (see below). However, if we find that any of the variables in the tables in sections 4.2 and 4.3 and in the table are imbalanced between the randomisation groups, or if any behaviours changed significantly over time (see table above), one or two additional variables may be added to the models.

Adherence: Adherence to the study interventions was assessed at the D7, M1 and M2 visits by structured interviewer-administered questionnaire, review of a diary card that the participant completed in between

study visits, review of returned used packaging and unused product, and by asking the participant to complete a self-rating adherence scale. These different sources of adherence data will be triangulated to arrive at an overall level of adherence (between 0-100%) for each participant between the Enrolment and D7 visits, D7 and M1 visits, M1 and M2 visits, and the Enrolment and M2 visits. Women were allowed to cease product use during menstrual bleeding and these days will therefore not be taken into account. Adherence will be plotted in a line graph for randomisation groups 2, 3 and 4 with study visits (D7, M1, and M2) on the horizontal axis and the adherence percentage on the vertical axis. In the GEE models, only one overall adherence measure (% between the Enrolment and M2 visits) will be used, with the adherence level for women in Group 1 (who did not use any study product) set at 100%.

7. Analysis of follow-up data: primary safety outcomes

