 - Urine specimens: Initial processing and storage for urine microbiome analyses in Europe (if funding permits; see 8.2).

Use of Amsel criteria: As noted in the introduction, one of the four Amsel criteria is the presence of vaginal discharge, and we may therefore miss asymptomatic cases of BV if we use the Amsel criteria instead of Nugent scoring. This is not a problem for the women themselves because asymptomatic BV is normally not treated, but it is a missed opportunity for this study. We will closely monitor our Amsel data in the beginning of the study (compare the Amsel data with the Nugent data), and if warranted, we may decide to only use the three laboratory Amsel criteria to guide enrolment and treatment decisions. In that case, BV by Amsel criteria would be defined as 2 of the 3 laboratory criteria throughout this protocol.

6.5 Follow-up visits Day 7, Month 1 and Month 2

Follow up visits in the clinical trial will take place at Day 7 (7 days after start of the intervention), Month 1, Month 2 (cessation of the intervention), and Month 6 (4 months after cessation of the intervention).

The following procedures will take place during the Day 7, Month 1 and Month 2 follow up visits:

- 1. Confirmation of contact information. Women who are menstruating at the time of a study visit will be asked to return for completion of visit procedures after they have finished menstruating.
- 2. Face-to-face interview (update since the last study visit on: current medications, contraception, genital symptoms, sexual behaviour, vaginal practices, penile hygiene practices of male partners, having been diagnosed and/or treated for STIs/BV/vaginal candidiasis or other medical conditions, adverse events/social harms, and acceptability of and adherence to the interventions).
- 3. Speculum examination with collection of specimens: vaginal specimens for vaginal pH, wet mount, Gram stain Nugent scoring, TV culture and VMB and biofilm assessments at UoL, and a CVL to store for additional VMB assessments at UoL. If the participant has signs or symptoms of a reproductive tract infection, specimens will be collected for diagnostic testing as described for the screening visit.
- 4. Counselling with as main aim to address any questions or concerns the participant may have about her intervention. At the Month 2 visit, the intervention will be terminated.
- 5. Reimbursement, and scheduling of the next visit;

- 6. Participant leaves the RU clinic;

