4.3 Other baseline characteristics by randomisation group (collected at Enrolment)

Vaginal practices	Group 1 N=17	Group 2 N=17	Group 3 N=17	Group 4 N=17	Total N=68
Weekly frequency of washing body (median, IQR)					
Ever washing the genitalia, and if yes, location of					
washing (n % per category) ¹					
- Yes, outside only					
- Yes, both inside and outside					
- Yes, inside only					
- No					
Weekly frequency of cleaning inside the vagina					
(median, IQR)					
Timing of cleaning inside the vagina (n % per category) ²					
- Before sex					
- After sex					
- While bathing					
- During/after menses					
- Other (described in a footnote)					
Vaginal practices in the past 12 months, other than					
vaginal practices to manage menses (n % per category) ²					
- Water only using fingers					
 Water and soap using fingers 					
 Water with paper/cloth/cotton wool 					
 Water and soap with paper/cloth/cotton wool 					
 Paper, cloth, cotton, wool without liquid 					
- Traditional herbs, stones, or powder					
- Western vaginal medicine					
 Other (described in a footnote) 					
- No vaginal practices					
Practices to manage menstrual blood or spotting in the					
past 12 months (n % per category) ²					
- Tissue, toilet paper, paper, cloth or cotton wool put					
inside the vagina					
- Tissue, toilet paper, paper, cloth or cotton wool					
placed in underwear					
- Sanitary pad					
- Tampon					
 Water, without soap, inside the vagina 					
 Water, with soap, inside the vagina 					

- Other (describe in a footnote)					
- Nothing was used					
- Did not have menses in past 12 months					
Used anything inside the vagina other than plain water					
in the last two weeks (n/N %)					
If yes, what was used (n/N % per category) ¹					
- Soap					
- Soap - Paper/cloth/cotton wool					
- Tampon					
- Traditional herbs, stones or powders					
- Western vaginal medicine					
- Other (described in a footnote)					
	Group 1	Group 2	Group 3	Group 4	Total
Menses	N=17	N=17	N=17	N=17	N=68
Regular menstrual cycle (n % per category)					
- Yes					
- No, irregular					
- Amenorrhea due to hormonal contraception					
- Amenorrhea due to other reason (described in a					
footnote)					
Duration of bleeding(median, IQR)					
Amount of bleeding (n % per category)					
- Light					
- Moderate					
- Heavy					
History of painful periods (n %)					
Self-reported vaginal sex during menses in the past 12					
months (n %)					

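### The SAP 6.4 change table tests sex during menses on what appear to be unequal recall windows, so a fall is expected without any change in behaviour; the partner row may have a similar problem

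*SAP*

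**What the plan says.** SAP 6.4 introduces the table with "We will assess any behavioural changes over time in the total study population as follows". The columns are baseline, M2, M6 and a single p-value. The footnote names the tests: "McNemar's test for binary or categorical variables and Wilcoxon test for medians". The text does not say which pair of visits the p-value compares.

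The result has one stated use. Alongside CT/NG infection and adherence, the SAP says that "if any behaviours changed significantly over time (see table above), one or two additional variables may be added to the models".

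Two rows matter most:

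- **Sex during menses.** The 6.4 row, "If no amenorrhea, any vaginal sex during menses (n" %), gives no recall period. The only baseline version in the SAP is in the 4.3 table: "Self-reported vaginal sex during menses in the past 12" months. For Day 7, Month 1 and Month 2, protocol 6.5 describes the interview as an "update since the last study visit on: current medications, contraception, genital symptoms, sexual behaviour, vaginal practices" and further topics. Protocol 6.6 keeps the same topics at Month 6.
- **Sex partners.** One row carries two definitions: "Number of sex partners in last month at baseline or per" month during the follow-up period. The SAP does not say how the monthly figure is computed.

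A third row, on a new main partner in the period, is marked not applicable at baseline, so only M2 and M6 can be compared.

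**The concern.** A yes/no item asking whether something ever happened in a period rises with the length of the period. If baseline covers 12 months and follow-up covers 1 to 4, the yes proportion is lower at follow-up even when no woman has changed. McNemar's test then rejects because of the window, and another paired test on the same answers would have the same fault.

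SAP 6.4 gives this p-value a role in choosing covariates. It says that power is too low to adjust for many confounders and allows only one or two extra variables. A window artefact could take one of those places.

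**Working it through.** The documents state no rate, power or sample size for this comparison, so there is no figure of the plan to reproduce. The check asks what the test does when behaviour is constant.

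**Inputs from the documents**
- Baseline window for sex during menses: 12 months (SAP 4.3).
- Follow-up window: since the last visit (protocol 6.5 and 6.6). That is about 1 month at M2 (M1 to M2), or 2 months if the M2 column covers enrolment to M2, and 4 months at M6.
- Women attending: 66 at M2 and 64 at M6 (SAP 3.1). The number without amenorrhoea is not given.

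**Assumptions**
- One cycle per month.
- A fixed per-cycle probability p for each woman. Its mean ranges from 0.02 to 0.20, and the between-woman correlation ρ from 0 to 0.6 (beta-binomial).
- n = 40 or n = 66. The second is slightly above the 64 seen at M6.
- Two-sided 5% level. SAP 6.4 states none; 0.05 is used elsewhere in the SAP.

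**Step 1: expected proportion.** P(any over k cycles) = 1 − (1 − p)^k, which rises with k for every p between 0 and 1. With p = 0.05 and no variation between women:
- Baseline, k = 12: 1 − 0.95^12 = 46%
- M2, k = 1: 5%; k = 2: 1 − 0.95² = 9.75%, about 10%
- M6, k = 4: 1 − 0.95⁴ = 18.5%

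Variation between women narrows the gap but does not reverse it. At mean 5%, ρ = 0.3 gives 21% at baseline, 5 to 8% at M2 and 13% at M6. With ρ = 0.6 the figures are 12%, 5 to 7% and 9%.

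**Step 2: how often exact McNemar rejects with no true change** (mean p = 0.05, 3,000 simulated trials per setting)

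| n | ρ | M2, 1 cycle | M2, 2 cycles | M6, 4 cycles |
|---|---|---|---|---|
| 66 | 0 | 100% | 100% | 89% |
| 66 | 0.3 | 93% | 74% | 34% |
| 66 | 0.6 | 32% | 14% | 3% |
| 40 | 0 | 99% | 94% | 69% |
| 40 | 0.3 | 61% | 38% | 13% |
| 40 | 0.6 | 6% | 1% | 0% |

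Over all settings the rate runs from about 0 to 100%. With equal windows (1 cycle at both visits) it is 0 to 3% throughout.

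**Step 3: partner row.** Suppose the monthly figure means distinct partners divided by months. With s steady partners and λ new partners per month, the last-month count is s + λ, and the figure over T months is s/T + λ. The artefact is a fall of s(1 − 1/T).
- One steady partner and no others: 1.0 becomes 0.5 (T = 2) or 0.25 (T = 4).
- One steady partner plus 0.5 new per month: 1.5 becomes 1/4 + 0.5 = 0.75 (T = 4).
- One steady partner plus 2 new per month, simulated with n = 64: the median falls from 2.9 to 2.2 (T = 4), and Wilcoxon rejects in 95% of trials.
- With a one-month window there is no shift, and rejection is at most about 5%.

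**Step 4: weekly frequency of vaginal practices.** A constant weekly rate observed over windows of different length gave rejection in 5 to 6% of trials, which is nominal. Window length does not move this row.

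**The case against.** The strongest reply is that the follow-up window for sex during menses is inferred. The 6.4 row states none, the protocol's interview sentence is a general list that does not name the item, and the questionnaire is not in the documents. This stands as a limit on certainty. Still, 12 months is the only documented baseline window, and the only documented follow-up wording is since the last visit.

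Three stronger readings are tempting, and the documents do not support them.

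- **That several behaviours are shown to shift by construction.** Of the 15 rows, 11 are current-status, fixed-window or bleeding-duration items. Vaginal practices is already a weekly rate; what is unclear there is its baseline window and its match to the 4.3 wording. New main partner has no baseline value, and a longer M6 period would push it up. The partner row shifts only under one reading of an undefined term, and a monthly figure may be meant as a step towards a common unit.
- **That a fall will be read as a counselling effect.** All four groups are counselled, so a reader might infer this. But the SAP never presents these tests as an assessment of counselling. Their stated use is covariate selection.
- **That the treatment comparison is biased.** The tests pool the whole study population and do not themselves distort a contrast between groups. Adding a covariate is optional.

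The objection that the rejection rates rest wholly on assumed behaviour is also right, which is why only the range is given.

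**Conclusion.** The concern holds for one row and conditionally for a second. For sex during menses, a fall in expectation follows if the follow-up item covers the time since the last visit, as the protocol wording implies. The direction does not depend on the assumed rate, provided that at least some women have a per-cycle chance between 0 and 1. The size does: 46% against 5 to 10% and about 18 to 19% is one illustration, and the chance of a falsely significant result could be almost anything. For partner numbers, the shift occurs only if the monthly figure is distinct partners divided by months.

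The practical harm is a misleading p-value in a supporting table and possibly an unneeded covariate in the adjusted GEE models. The incidence rate and rate ratio analyses in SAP 6.1 to 6.3 do not use the table. Severity is minor.

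**What to change.** Amend SAP 6.4 as follows:

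1. State the recall window of each timed item at each visit, taken from the questionnaires.
2. Report sex during menses descriptively, without a p-value, unless answers over equal windows are available.
3. For partner numbers, use a last-month count at every visit if it was collected. Otherwise define the monthly figure, show baseline and follow-up separately, and give no p-value.
4. Compare new main partner between M2 and M6 only per unit of time, or describe it without a test.
5. State that an item with unequal windows cannot trigger an additional GEE covariate.

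This needs SAP wording only and no new data. The cost is fewer rows with a tested change over time. Rows with a fixed recent window or current status keep their tests.
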